#### **5.5 Early Termination Visits**

After the completion of Week 14, or at the termination for patients who discontinue from the trial prematurely, we will conduct the following procedures: physical exam, vital signs and weight, electrocardiogram, monitor adverse events and concomitant medications, obtain blood samples for CBC, blood chemistry, obtain a urinalysis (and a pregnancy test for women), Urine drug screen and urine buprenorphine and norbuprenorphine levels, CGI, Timeline followback, and system usability screen (SUS). At the completion of the trial patients will be referred to MAT in the community, or if they decline they will receive a tapering dose of Suboxone for one week.

#### **5.6 Efficacy Evaluations (only if applicable)**

For the ROD group, we will calculate the within-patient proportion of study days on which video captured adherence, as per protocol.

We will use a combination of self-report and (nor)buprenorphine levels to classify patients in the AC group as adherent or non-adherent for each study day to compare their rates of adherence to the (video-verified) rates in the ROD group. These comparisons will give a direct estimate of the improvement in adherence likely to be observed between the proposed method and standard methods.

Rates of illicit opiate use will be compared between the groups using combinations of urine drug screens (UDS) and TLFB self-reports obtained at each visit.

#### **5.7 Pharmacokinetic Evaluation**

Patients will provide a urine sample at each office visit that will test for quantitative buprenorphine and norbuprenorphine levels.

#### **5.8 Genetic Testing**

Not applicable

#### **5.9 Safety Evaluation (only if applicable)**

Adverse events will be monitored at each visit. Concomitant medications will be queried and recorded at each visit. Safety laboratory measures include, complete blood count (CBC), blood chemistries, urinalysis, urine pregnancy tests (for women), EKG.

### **6 Statistical Plan**

#### **6.1 Sample Size and Power Determination**

One target of the study is to estimate the proportion of participants in the ROD group who adhere with their medication schedule for, say, 80% or more of their treatment days. If 90% of the 20 participants adhere, then our data will yield a 95% confidence interval of (68%, 98%) for the proportion adhering; if 95% are adherent, then our confidence interval will be (72%, 99%).

CONFIDENTIAL

For the longitudinal comparisons of quantitative (nor)buprenorphine levels, transformed so that a linear model is appropriate, we use the methods of Hedeker and colleagues. For an alpha level of 0.05, and assuming a within subject correlation of 0.4, and dropout of 10%, the sample size provides 80% power for a standardized linear group by time effect of  $d=0.65$ . Thus, the study is powered for medium to large effects in quantitative buprenorphine levels.

## **6.2 Statistical Methods**

For the ROD group, we will calculate the within-patient proportion of study days on which video captured adherence, as per protocol. We will use these data to compare observed adherence rates in this group to rates reported in prior studies. The primary comparison between the groups will use the creatinine normalized weekly quantitative urine levels for buprenorphine and norbuprenorphine. Exploratory analyses include the following: We will use a combination of self-report and (nor)buprenorphine levels to classify patients in the AC group as adherent or non-adherent for each study day, and use mixed effects logistic regression models to compare their rates of adherence to the (video-verified) rates in the ROD group. Rates of illicit opiate use will be compared between the groups using combinations of urine drug screens(UDS) and TLFB self-reports obtained at each visit. The ASI, CGI, and HAM-D scales are obtained monthly. To assess usability and acceptability of the ROD protocol and text messaging application, [name] will conduct semi-structured interviews and analyze data from the Systems Usability Scale (SUS) at the final office visit.

## **6.3 *Control of Bias and Confounding (if applicable, typically observational study or if randomization is not taking place)***

Subjects will be randomly assigned to the two groups

### **6.3.1 Baseline Data**

Baseline and demographic characteristics will be summarized by standard descriptive statistics (including mean and standard deviation for continuous variables such as age and standard percentages for categorical variables such as gender).

### **6.3.2 Analysis of Primary Outcome of Interest**

The primary comparison between the groups will use the creatinine normalized weekly quantitative urine levels for buprenorphine and norbuprenorphine. For each response, we anticipate that a response transformation, such as the log transform, will yield responses appropriate for group comparisons based on linear mixed effects models, but we will consider generalized linear mixed effects models if necessary. Comparisons of BIC statistics across different covariance structures will be used to select the best model for within subject correlations – typically a model with random intercept and ar(1) residual correlations provides a good fit. The main explanatory variable will be a binary indicator for group (ROD vs AC). Time will be regarded as a continuous scale, and linear, quadratic or spline trends will be used as necessary, with group by time interactions examined for significance. Our primary analyses will examine the two sets of responses (buprenorphine and norbuprenorphine) separately, but we will also consider bivariate mixed effects models with cross-correlation structure to assess strength of dependence and concordance between the two sets of measures. These analyses will be performed using PROC GENMOD in SAS.

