## **3 Investigational Plan**

Forty patients with OUD, who are not currently prescribed buprenorphine, will be recruited through the University of Pennsylvania's Center for the Studies of Addiction (CSA), an outpatient substance abuse treatment facility. Potential participants will be screened for physical and psychological appropriateness for inclusion in the study using the CSA standard intake procedures. This includes a psychosocial diagnostic evaluation, a medical exam, urine and blood tests, and an EKG (see Measures for full description of screening assessments). Participants who are appropriate for the trial will be inducted onto Suboxone® using standard office based induction as described in the ASAM National Practice Guideline for the Use of Medications in the Treatment of Addiction Involving Opioid Use (Kampman and Jarvis 2015).

All patients will receive buprenorphine (Suboxone®; up to 24 mg daily) and will be randomly assigned to one of two groups. The experimental group (n=20) will receive daily remote observed dosing (ROD) via a secured video platform that records dosing using study-provided smartphones (approximately 5 minutes each session). ROD videos will be monitored daily for compliance. The attention control group (AC, n=20) dosing will not be observed. All subjects will attend 2 weekly study visits (3 study visits during the induction phase in Week 2). Study visits starting in Week 3, after the Induction phase, will consist of counseling in the form of weekly Medication Management (MM); buprenorphine distribution with medication management; and a urine screen. Study visit 4 will consist of a urine screen and phone management task (downloading study related videos) for those randomized to the Remote Observed Dosing Group.

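### The random intercept plus AR(1) model expected in 6.3.2 understates the error of the group-by-time effect powered in 6.1 if patients' trends differ within an arm

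*Combined protocol and SAP*

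**What the plan says.** Section 6.3.2 compares the arms on creatinine-normalised weekly buprenorphine and norbuprenorphine, transformed if needed, with linear mixed effects models. On the covariance it says: "Comparisons of BIC statistics across different covariance structures will be used to select the best model", and adds that "typically a model with random intercept and ar(1) residual correlations provides a good fit". The candidates are not listed. The group indicator is the main explanatory variable, time is continuous, and group-by-time interactions are to be tested. The section gives no robust standard error and no degrees-of-freedom method, and it names PROC GENMOD as the software.

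Section 6.1 claims "80% power for a standardized linear group by time effect" of d = 0.65. The stated inputs are 5% alpha, 10% dropout and one correlation ("assuming a within subject correlation of 0.4"). No between-patient variance of slopes appears. Section 3 gives 20 patients per arm.

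**The concern.** A group-by-time effect is a difference between two mean slopes. Its error therefore has two parts: noise around each patient's own line, and real variation between patients in how steep that line is. More urine samples per patient reduce the first part. Only more patients reduce the second, and there are 20 per arm.

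A random intercept lets patients differ in level. AR(1) residuals let neighbouring samples resemble each other. Neither represents patients who drift steadily in different directions over 12 weeks. If such drift exists, the fitted standard error is too small, the interval too narrow and the 5% level exceeded, on the one between-group effect for which the plan states a power. The power in 6.1 would be too high for the same reason.

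**Working it through.** **Inputs from the documents.** 20 per arm (section 3); alpha 0.05, correlation 0.4, dropout 10%, d = 0.65 (section 6.1); weekly levels over 12 weeks, so 12 values (sections 6.2 and 6.3.2). **Assumed.** A two-sided test, and the SD of patients' true drift from first to last value, τ, in units of the baseline SD. The documents give no value for τ, so 0 to 1.0 was tried.

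**Step 1: reproduce 6.1.** Code time from 0 to 1 over 12 equally spaced values. The centred sum of squares is 143/121 = 1.182. With correlation 0.4 the residual variance is 0.6, so one patient's slope has error variance 0.6/1.182 = 0.508. With n per arm, SE = √(2(τ² + 0.508)/n) and power = Φ(0.65/SE − 1.96). At τ = 0:

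- n = 20: SE = 0.225, power 82%.
- n = 18: SE = 0.238, power 78%.
- n falling linearly from 20 to 18: power 80.1%.

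The stated 80% is reproduced, but only with τ = 0. Using 24 values gives 96.7%, so 12 values is the reading that fits 6.1.

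**Step 2: power with slope variation.** The same formula with n = 18, beside the linear-dropout version:

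| Drift SD τ | SE, n = 18 | Power, n = 18 | Power, linear dropout |
|---|---|---|---|
| 0 | 0.238 | 78% | 80% |
| 0.25 | 0.252 | 73% | 75% |
| 0.5 | 0.290 | 61% | 63% |
| 0.75 | 0.345 | 47% | 49% |
| 1.0 | 0.409 | 36% | 37% |

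**Step 3: why the test over-rejects.** At τ = 0.5 the true slope variance per patient is 0.25 + 0.508 = 0.758. A model that ignored the drift entirely would use 0.508. Its SE would be too small by √(0.758/0.508) = 1.22, so its nominal 1.96 would act as 1.96/1.22 = 1.60, which gives 10.9% rejection. In practice the AR(1) term absorbs part of the drift, so the random intercept plus AR(1) model does somewhat better, as step 4 shows.

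**Step 4: type I error of the expected model.** Null effect, 12 values, 20 per arm, complete data, nominal 5%. Each cell gives the large-sample value, then the simulated value (REML, 1,500 trials, simulation error about 0.6 to 1 point):

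| Drift SD | Independent residuals | AR(1) residuals, 0.4 |
|---|---|---|
| 0 | 5.0 / 5.5% | 5.0 / 5.1% |
| 0.25 | 6.0 / 6.6% | 5.5 / 5.2% |
| 0.5 | 8.9 / 8.1% | 6.8 / 6.9% |
| 0.75 | 12.6 / 13.5% | 8.6 / 8.5% |
| 1.0 | 16.0 / 16.4% | 10.3 / 11.1% |

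Smaller separate simulations at 0.5 and 0.75 gave 9.5% and 12.4% (800 trials), and 10.3% and 13.7% (300 trials), with independent residuals.

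**Step 5: does a random slope repair it?** In large samples the error returns to 5.0%. In a 500-trial check, a random slope with small-sample degrees of freedom gave 3-6%. In the batches used for step 6 it gave 3-8%.

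**Step 6: does BIC repair it?** With independent residuals (500 trials per setting) and slope models among the candidates, BIC picked one in 23%, 69% and 96% of trials at drift SD 0.5, 0.75 and 1.0. The selected test then rejected 12.2%, 10.0% and 6.2%. With no slope candidates it rejected 14.0%, 16.2% and 17.4%. At 0.5 this batch ran high: the fixed random intercept plus AR(1) model rejected 12.6% there, against 8.1% in step 4. With AR(1) residuals of 0.4 (400 trials) and slope candidates, the selected test rejected 6.2% at 0.5 and 5.5% at 1.0. A separate check with random slope plus AR(1) as a candidate found a slope chosen in 14-38% of trials at 0.5 and 56-87% at 0.75, with about 6-7% rejection after selection.

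**The case against.** **The plan does not commit to this model.** The quoted clause says what usually fits; BIC decides, and no random slope is excluded. This stands, so a reader should not infer that the trial's error rate is certainly inflated. What remains is that slope models are not listed, and without them BIC cannot choose one.

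**BIC could find the slope.** A reader might infer that BIC never picks a slope when residuals are autocorrelated. That is not so once random slope plus AR(1) is a candidate (step 6). The supportable statement is that it often misses moderate slope variance with 40 patients.

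**Larger inflation, from 24 samples.** Urine is collected twice weekly, and with 24 values the large-sample error at drift SD 0.5 to 1.0 is 13.4-26.6% (independent residuals) or 8.9-16.4% (AR(1) 0.4). But 6.2 and 6.3.2 specify weekly levels for the primary comparison, and 6.1 reproduces with 12 values, so these are not the figures for the plan as written.

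**The named software would avoid the problem.** PROC GENMOD fits GEE and has no random effects. GEE with robust errors showed no drift-related excess: 5.3-7.9% across all drift SDs in the 1,500-trial runs, including zero drift, which is small-sample bias. This stands as a further point against the section: the text describes a mixed model that the named procedure cannot fit, and it mentions no robust error.

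**The slope SD is assumed, and the scope is limited.** Both points stand. The documents give no slope SD. Section 1.1 shows wide differences in adherence between patients, not in trends. Nothing here shows a fault in the test of the average group difference, and the trial describes its aim as preliminary efficacy.

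**Conclusion.** The concern holds as a conditional one. If the analysis ends in the model that 6.3.2 expects, with model-based errors, and patients' trends differ within an arm, the group-by-time test exceeds its 5% level. With 12 weekly values the rate is about 5-7%, 7-10%, 8-14% and 10-16% at drift SD 0.25, 0.5, 0.75 and 1.0. The excess is small at 0.25 and moderate at 0.5. Near 1.0 it reaches two to three times the nominal level. The 80% in 6.1 holds only with no slope variation.

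The result rests on an assumed drift SD, a linear trend and complete data; dropout entered the power calculation only. It is an inexpensive improvement to the plan, not a defect that undermines the trial.

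**What to change.** In 6.3.2:

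- Include a random slope for time in every model that tests group by time. Let BIC choose only the residual structure, from a listed set, and use small-sample degrees of freedom such as Kenward-Roger.
- If a GEE is what is intended, say so and use robust standard errors with a small-sample correction.
- Name a procedure that can fit the chosen model; PROC GENMOD cannot fit random effects.
- If a quadratic or spline trend is used, say how between-patient variation in that trend is handled, since a linear random slope does not cover it.

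In 6.1, state that the 80% assumes no variation in patient slopes, and give power of about 75%, 61-63% and 47-49% at drift SD 0.25, 0.5 and 0.75 (73% at 0.25 if 18 per arm is used throughout).

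The cost is a few lines of text and one model line. The real price is a wider interval and a less favourable stated power. No visit, sample or patient is added.

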### **3.2 Allocation to Interventional Group**

Participants will be randomized into one of two study groups based on proportion of use of prescription opiates and heroin, gender, and prior Suboxone® treatment.

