### **5.4           *Subject Withdrawal***

Subjects may withdraw from the study at any time without impact to their care. They may also be discontinued from the study at the discretion of the Investigator for lack of adherence to intervention or study procedures or visit schedules, AEs, or due to worsening of opioid use disorder. The Investigator may also withdraw subjects who violate the study plan, to protect the subject for reasons related to safety or for administrative reasons. It will be documented whether or not each subject completes the study. Subjects who withdraw early will have one final visit to collect final evaluations and assess adverse events.

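### Section 6.3.2 assigns mixed models to PROC GENMOD, which cannot fit them, and its primary model omits the three factors used for allocation

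*Combined protocol and SAP*

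**What the plan says.** Section 6.3.2 bases the primary group comparison on creatinine-normalised urine buprenorphine and norbuprenorphine. After transformation, each is to be analysed with linear mixed effects models, or generalised linear mixed models if needed. On the covariance it says "Comparisons of BIC statistics across different covariance structures will be used to select the best model for within subject correlations", and adds that "typically a model with random intercept and ar(1) residual correlations provides a good fit". It goes on: "we will also consider bivariate mixed effects models with cross-correlation structure". It closes with "These analyses will be performed using PROC GENMOD in SAS". No other section names a different procedure.

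The explanatory terms named in that section are the group indicator (described as the main one), a time trend and the group-by-time interaction. No baseline covariate is named there or elsewhere in Section 6.

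Section 3.2 says that participants are randomised "based on proportion of use of prescription opiates and heroin, gender, and prior" Suboxone treatment. It does not say whether this means stratified blocks, minimisation or something else, nor how the factors are coded.

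Section 6.1 powers a group-by-time effect of d = 0.65: "assuming a within subject correlation of 0.4, and dropout of 10%, the sample size provides 80% power".

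**The concern.** There are two separate matters.

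First, the named software and the described model are incompatible. Whoever programs the primary analysis must depart from one or the other, and the plan does not say which. That choice is better made on paper before the data are seen.

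Second, factors are usually chosen to guide allocation because they are thought to matter for outcome. If they do, and the model ignores them, their contribution stays in the error term. With 20 patients per arm, the comparison of group levels then loses power that adjustment would recover. If allocation also balances the factors, the unadjusted standard error is too large for the design and the test becomes conservative.

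**Working it through.** **1. Model against procedure.** This step rests on general knowledge of the software; the documents do not discuss it.

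| Section 6.3.2 asks for | PROC GENMOD offers |
|---|---|
| Random intercept plus AR(1) residuals | GLMs and, through REPEATED, marginal GEE; no random effects |
| BIC across covariance structures | No likelihood BIC for GEE fits (QIC instead); the printed BIC belongs to the independence GLM |
| Generalised linear mixed model if needed | Not available |
| Bivariate mixed model | Not available |

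Every modelling element belongs to a mixed-model procedure. Only the procedure name does not fit.

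**2. The plan's own power figure.** From the documents: 20 per arm (Section 3), alpha 0.05, correlation 0.4, dropout 10% and d = 0.65 (Section 6.1). Assumed: a two-sided test, 12 weekly values, compound symmetry, retention falling linearly from 100% to 90%, and a difference rising linearly from 0 to 0.65 SD.

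- Contrast c runs from -5.5 to 5.5 in steps of 1, so the sum of c² is 143 and c'μ = (0.65/11) × 143 = 8.45.
- V = Σ c_i c_j s_ij / √(r_i r_j) = 90.7.
- z = 8.45 / √(2 × 90.7 / 20) = 2.81, and power = Φ(2.81 − 1.96) = 80.1%.

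The stated 80% reproduces under these assumptions.

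**3. Effect of the factors on that slope.** The contrast weights sum to zero, so anything constant within a patient cancels. Simulation with dropout agrees. At R² = 0 / 0.2 / 0.4, slope power is 78.4 / 78.5 / 78.5% unadjusted and 78.5 / 78.5 / 78.8% adjusted. R² is the share of between-patient variance that the factors explain. The documents give no value, so a range is used.

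**4. Effect on the comparison of group levels.** Here a constant 0.65 SD difference is assumed; Section 6.1 gives 0.65 only for the slope. With total variance 1 and complete data, the variance of a patient's mean is 0.4(1 − R²) + 0.6/12 after adjustment, and the standard error of the difference is √(2 × variance / 20).

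| R² | Variance | SE | Power, Φ(0.65/SE − 1.96) |
|---|---|---|---|
| 0 | 0.45 | 0.212 | 87% |
| 0.2 | 0.37 | 0.192 | 92% |
| 0.4 | 0.29 | 0.170 | 97% |

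Without adjustment, the test always uses SE 0.212. If allocation balances the factors, the true SE is 0.192 or 0.170. The effective critical value is then 1.96 × 0.212/0.192 = 2.16 at R² = 0.2, or 2.44 at R² = 0.4, which corresponds to type I error of about 3.1% or 1.5%.

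**5. Simulation.** This adds 4 of 40 dropping out at random, REML with Kenward-Roger degrees of freedom, and three binary factors (an assumption). Monte Carlo error is about 0.25 points for the balanced null results and 0.45 for power. Entries are for R² = 0 / 0.2 / 0.4.

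| Allocation | Quantity | Unadjusted (%) | Adjusted (%) |
|---|---|---|---|
| Balanced | Type I error | 5.4 / 3.5 / 2.0 | 5.2 / 5.2 / 5.3 |
| Balanced | Power | 84.1 / 85.6 / 87.7 | 83.6 / 89.7 / 95.2 |
| Simple | Type I error | 4.8 / 4.9 / 5.1 | 5.0 / 5.0 / 4.9 |
| Simple | Power | 84.6 / 84.7 / 84.6 | 81.1 / 88.1 / 94.2 |

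A separate recomputation with balanced allocation gave power of 87% against 91% at R² = 0.2, and 90% against 96% at R² = 0.4.

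**6. Sensitivity.** With AR(1) residual correlation of 0.3 (assumed) and balanced allocation, power is 81.5 / 83.8 / 85.5% unadjusted and 80.9 / 87.0 / 92.7% adjusted. Sections 6.2 and 6.3.2 speak of weekly levels, but Sections 3.3 and 5.2.3 collect them twice weekly. With 24 values, blocks of 4 and R² = 0.2, type I error is 3.2% unadjusted, and power is 88.4% unadjusted against 92.3% adjusted. The pattern does not depend on the 12-value reading.

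**The case against.** The best reply is that the GENMOD sentence is a slip. Model class, expected covariance and selection rule are all stated, and a statistician would meet the problem at the first line of code. That stands. It limits the weight of the point, but the sentence still cannot be carried out.

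Three stronger readings are tempting, and the documents do not support them.

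- **That the primary test is liberal.** An exchangeable GEE with uncorrected robust z-tests gives slope type I error of about 6.2-6.3%, against 4.8-4.9% for the mixed model. This arises only if the written mixed model is abandoned for GEE, which the text does not intend. It is also specific to the Wald test: in a complete-data check the score test gave 5.1% against 6.2% for Wald.
- **That withdrawal biases the result.** Section 5.4 allows patients to be "discontinued from the study at the discretion of the Investigator for lack of adherence to intervention or study procedures or visit schedules", and a GEE can be sensitive to this. Again that requires GEE, and the documents give no withdrawal rule from which a bias could be calculated.
- **That the 80% in Section 6.1 is refuted, or is secured.** It reproduces under compound symmetry with 12 values. With a random intercept of variance 0.4 plus AR(1) 0.3 residuals, the same formula gives V = 141.0, z = 8.45/√14.10 = 2.25 and power of 61%. The present point neither disputes nor endorses the 80%.

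On the factors, it is fair to object that calling group the main explanatory variable leaves room for others, that R² and the constant 0.65 SD difference are assumptions, that the allocation method is unstated, and that the study tests preliminary efficacy only. All of this stands. Adjustment is therefore a gain in precision and not the repair of a bias.

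**Conclusion.** Both parts hold, at moderate weight. The procedure named in Section 6.3.2 cannot fit the models described there and should be corrected before analysis. The intended model is not in doubt.

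Leaving out the allocation factors does not bias the estimate. What it costs in the comparison of group levels depends on how prognostic the factors are: at R² of 0.2 to 0.4, about 85-90% power unadjusted against 88-96% adjusted. The conservative type I error, about 3.5% falling to 2%, applies only if allocation balances the factors. At R² = 0 there is nothing to gain. The conclusion that adjustment leaves the slope test essentially unchanged does not depend on R².

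**What to change.** In Section 6.3.2, replace PROC GENMOD with PROC MIXED for the linear mixed models, preferably with Kenward-Roger degrees of freedom, and name PROC GLIMMIX in case a generalised linear mixed model is needed. Add a sentence making opioid-type use, gender and prior Suboxone treatment fixed effects in both the buprenorphine and norbuprenorphine models, coded as in the randomisation. Section 3.2 should state that coding and the allocation method, because the new sentence depends on them.

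If GEE was meant after all, the section needs a named working correlation, a small-sample correction, and QIC in place of BIC.

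No new data are needed, since the factors must be known in order to allocate. Adjustment uses about 3 degrees of freedom if each factor is one term. If the factors prove not to be prognostic, the simulated loss of power is 0.5 points with balanced allocation (84.1 to 83.6%) and 3.5 points with simple allocation (84.6 to 81.1%).
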